- We will create online/digital training programs for laboratory workers, health care providers, and clinic staff regarding CRAG screening and pre-emptive treatment. Alternatively, we will partner with existing initiatives such as Project ECHO (continuing professional education and clinical mentoring via zoom video conferencing). These educational programs will be implemented at clinics to evaluate whether gaps in the cascade of care can be minimized.
- We will create refresher training for lab workers, health care providers, and clinic staff regarding CRAG screening and pre-emptive treatment, and measure if more frequent training sessions improve adherence to national protocols and patient outcome.
- Finally we will create patient education materials in the form of posters that can be hung in clinic waiting rooms, short presentations that can be performed by community healthcare workers in clinic waiting rooms/ as part of focus groups, and digital training programs for patients. We will measure overall clinic adherence to national protocols and patient outcomes. Sample educational materials below.

Intervention 3: Determine benefit of enhanced methods to deliver CD4 and CRAG results

- a) SMS may be used for clinic appointment reminders, medication adherence reminders, and general information, as a potential method to enhance retention in care of CRAG+ persons. SMS may be used by clinics to enhance the cascade of care, for example, to report anticipated fluconazole stockouts, or to remind providers to perform TB screening for those with advanced HIV disease.
- b) Reports for each district and facility managers with line list of CRAG+ patients, and those with a CD4<100 without CRAG testing (compare outcomes in districts/ facilities with Result for Action reports vs. no Result for Action reports)
- Intervention 4: Enhanced antifungal therapy based on CRAG titre. After years 1 and 2, outcomes of those with high/low CRAG titres will have been summarized. We hypothesise that those with high CRAG titres would have higher mortality and would be at higher risk for breakthrough meningitis, as seen in multiple other studies.

If this is the case, we may then select a small number of high volume sites to perform CRAG titres in real time, and recommend enhanced antifungal therapy for those with high CRAG titres. Please note: This will be a separate ethics committee submission and will include informed consent from participants.

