8.1 Statistical Analysis Plan

The rate (with 95% confidence interval) for the primary and secondary events will be estimated overall and for pre-specified subgroups during the first 2 years of the study. Those rates will subsequently be compared with the rates after programmatic changes have been made (during years 2-5) to increase the effectiveness of the national screening program.

For the subgroups we will also use time-to-event methods to compare the primary and selected secondary endpoints. The table below reports detectable hazard ratios for the primary event with 80% and 90% power, assuming a two-sided alpha=0.05, 70% CM-free survival in the control group, and the stated number of subgroup participants. For example, if CSF CRAG titre data are available for 1200 participants (with 300 having a titre \geq 160), then we can detect a hazard ratio as small as 1.37, for an almost 10% difference in event-free survival.

Detectable Hazard Ratios for Subgroups					
(Assuming two-sided α =0.05 and 70% event-free survival in the control group)					
		80% Power		90% Power	
	N per		Proportion		Proportion
Subgroup	group	HR	Surviving	HR	Surviving
High CSF CRAG titre	300	1.37	0.61	1.44	0.60
(≥1:160)					
Control	900				
(CSF CRAG titre < 1:160)					

The a priori subgroups of interest are:

- High CRAG titres (\geq 1:160) vs. low titres (<1:160)
- Male vs. Female
- Pregnant vs. Non-pregnant
- Liver Disease (ALT>3x Upper Limit of Normal) vs. No liver disease

- Geographic Location (urban vs. rural)
- Timing of ART Initiation
 - On pre-existing ART
 - Initiated on ART before CD4/ CRAG results are known (same-day ART initiation in the context of universal HIV test-and-treat)
 - ART initiated at 2 weeks
 - ART initiated at >=4 weeks
- Clinic-level outcomes (i.e. cluster) based on proportion of CRAG+ persons receiving Lumbar Punctures.
- Duration of fluconazole use
- Fluconazole secondary prophylaxis vs. none

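### Section 8.1 compares event rates before and after the programme changes within subgroups, but four of the nine subgroup factors are defined by care that those changes may alter

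*Protocol*

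**What the plan says.** Section 8.1 states that rates of the primary and secondary events are "estimated overall and for pre-specified subgroups during the first 2 years of the study". The next sentence reads: "Those rates will subsequently be compared with the rates after programmatic changes have been made (during years 2-5". The natural antecedent of its opening words includes the subgroup rates.

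The a priori list in 8.1 has nine factors. Four concern care received:
- "Timing of ART Initiation" (pre-existing ART, ART started before results are known, at 2 weeks, at 4 weeks or later)
- "Clinic-level outcomes (i.e. cluster) based on proportion of CRAG+ persons receiving Lumbar Punctures"
- "Duration of fluconazole use"
- "Fluconazole secondary prophylaxis vs. none"

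Section 3 gives example interventions for Years 2-5. Intervention 1 may recommend lumbar puncture when the titre is 160 or more. Intervention 2 would "measure if more frequent training sessions improve adherence to national protocols and patient outcome". Under Intervention 3, "SMS may be used for clinic appointment reminders, medication adherence reminders, and general information", with retention in care as the aim. Section 3 also says that the final choice depends on what the first surveillance shows, and that intervention facilities will be compared with facilities without the intervention as well as with their own earlier results. No section fixes subgroup membership before the altered care, standardises case mix between periods, or limits the before/after comparison to baseline-defined groups.

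**The concern.** A before/after comparison within a subgroup is interpretable only if the label means the same kind of patient in both periods. If training or reminders lead more patients to complete fluconazole, some who would have been in a short-duration group in Years 1-2 are in a longer-duration group later. Both groups then have a different case mix because the intervention worked on the process of care. This is stage migration. Careful handling of exposure time within each period does not remove it, because the error lies in the comparison across periods.

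There is room for such movement: section 1.1 reports that 63% of CRAG+ persons were treated with fluconazole in Phase 1, and that 48% were lost to follow-up in a pilot. What is at stake is the reading of subgroup results in Years 2-5: an intervention with no effect, or a modest benefit, could appear harmful in both levels of a care-defined factor, or the reverse. The cost-effectiveness work in section 3 also stratifies effectiveness by secondary prophylaxis, so a misread shift could carry over.

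**Working it through.** **1. The plan's own figures.** Section 8.1 gives detectable hazard ratios of 1.37 (80% power) and 1.44 (90%) for 300 vs 900 participants with 70% control survival. With survival 0.70^HR (0.6135 and 0.5983), a two-proportion calculation gives power of 78.7% and 89.6%. These reproduce within 2 points and are not in dispute. They concern high vs low titre, not before vs after.

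**2. Sorting the nine factors.**
- Not defined by the altered care: titre, sex, pregnancy, liver disease, urban/rural.
- Defined by it, wholly or in part: ART timing (except pre-existing ART), clinic lumbar puncture proportion, fluconazole duration, secondary prophylaxis.

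**3. Migration with no intervention effect.** From 8.1: 30% failure (70% event-free survival). Assumed: 25% of patients at 20% risk, 50% at 30%, 25% at 40%, so the mean is 0.05 + 0.15 + 0.10 = 0.30. Group B receives the care and group A does not. Before the change, B is the low-risk stratum and A the rest:
- B = 20.0%
- A = (0.15 + 0.10)/0.75 = 33.3%

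Let a fraction f of the middle stratum move from A to B:
- A = [0.15(1−f) + 0.10] / [0.50(1−f) + 0.25]
- B = [0.05 + 0.15f] / [0.25 + 0.50f]

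| f | A after | B after | Overall |
|---|---|---|---|
| 0.2 | 0.22/0.65 = 33.8% | 0.08/0.35 = 22.9% | 30.0% |
| 0.5 | 0.175/0.50 = 35.0% | 0.125/0.50 = 25.0% | 30.0% |
| 1.0 | 0.10/0.25 = 40.0% | 0.20/0.75 = 26.7% | 30.0% |

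Both groups worsen while the overall rate does not move. Run in the opposite direction, both improve.

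**4. Chance of a false significant worsening.** Assume 1200 patients per period (borrowed from the titre example, not a planned period size). Then chance = Φ[(d − 1.96·se0)/se1], with se0 pooled and se1 unpooled. Example, B at f = 0.5: n = 300 and 600, d = 0.05, pooled rate (60 + 150)/900 = 0.233, se0 = 0.0299, se1 = 0.0291, giving Φ(−0.296) = 38%.

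| f | A | B |
|---|---|---|
| 0.2 | 4% | 15% |
| 0.5 | 10% | 38% |
| 1.0 | 55% | 64% |

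The formula counts only the worse direction, so the benchmark is 2.5% of a two-sided 5%. For A at f = 0.2 the other tail adds 1.5%, so the two-sided total is about 4.1% + 1.5% = 5.6%, close to nominal.

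**5. An extreme case.** Take equal thirds with event-free survival of 85%, 70% and 55% (mean 70%), with only the best third in the long-fluconazole group at first and the whole middle third moving into it.
- Long: 85% to (85 + 70)/2 = 77.5%; z = 0.075/√(0.85·0.15/400 + 0.775·0.225/800) = 3.24.
- Short: (70 + 55)/2 = 62.5% to 55%; z = 0.075/√(0.625·0.375/800 + 0.55·0.45/400) = 2.48.
- Overall stays at 70%. If everyone truly gained 3 points, both groups would still look 7.5 − 3 = 4.5 points worse.

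**The case against.** The strongest reply is that the before/after subgroup contrast rests on two words in 8.1. Elsewhere the subgroup analyses are between groups (for example prophylaxis vs none), the worked example is high vs low titre, and the Years 2-5 objective carries no subgroup clause. An SAP could say which subgroups enter which contrast. This supports calling it a wording problem, but does not remove it: the protocol itself states the comparison and the list, and nothing in it separates the care-defined factors.

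Some stronger inferences are not supported:
- **That every subgroup is compromised.** Five of nine factors are not defined by the altered care, and pre-existing ART is fixed beforehand.
- **That the main Years 2-5 conclusion is biased by this.** The overall rate is untouched by migration. Section 3 also adds concurrent facilities, and nowhere makes keeping an intervention depend on care-defined subgroup rates. Those facilities support the overall contrast. They do not cure migration within a subgroup, because movement caused by an intervention occurs only where it is applied.
- **That the interventions are designed to change exactly these factors.** They are examples. Only the lumbar puncture recommendation maps directly onto a listed factor, and there clinics, not patients, change category. Training and reminders could shift the others indirectly.
- **That large false-positive rates are expected.** Step 5 assumes perfect sorting by prognosis and complete movement of the middle third, and 8.1 gives no duration categories. At 20% movement one of the two groups stays near nominal.

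**Conclusion.** The point holds for four of the nine factors. As worded, 8.1 allows before/after differences within groups defined by later ART timing, clinic lumbar puncture proportion, fluconazole duration or secondary prophylaxis to be read as intervention effects, when they may reflect only who is in each group.

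The size cannot be known from the document. Under the assumptions in steps 3 and 4, the false-signal rates run from about 4%/15% to 55%/64%. They rest on three things that the protocol does not give: the risk mix, the share of patients who move, and 1200 patients per period. Both levels move the same way only when those who move have intermediate prognosis; otherwise the distortion takes another pattern. The patient-level model does not describe the lumbar puncture factor. The point should be corrected, but it does not threaten the overall before/after result.

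**What to change.** In section 8.1, state that before/after comparison of event rates is made for:
- the overall cohort, together with the concurrent non-intervention facilities described in section 3;
- subgroups fixed before the altered care: titre, sex, pregnancy, baseline ALT, urban/rural, pre-existing ART.

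ART started before results are known can be kept as a category fixed at the result date, so that same-day initiation stays in view, with the caveat that its case mix may change between periods.

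State also that before/after event rates within groups defined by later ART timing, fluconazole duration, secondary prophylaxis or post-intervention clinic lumbar puncture proportion are not interpreted as intervention effects. Use these groups for within-period description, and report their distribution before and after alongside the cascade outcomes already in section 2.2.2. For lumbar puncture, clinics may instead be classified by their Years 1-2 proportion and held in that class.

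This is a change of wording in the protocol or SAP and needs no new data. The downside is fewer before/after subgroup results.

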- 3) Integration with WHO universal HIV test-and-treat guidelines: South Africa adopted the WHO universal HIV test-and-treat guidelines in September 2016. While the National Department of Health has indicated that a baseline CD4 count should be ordered for all patients starting ART, in practice many patients are initiated on ART on the same day as HIV diagnosis, well before the baseline CD4 and reflex CrAg results are available. In KwaZulu-Natal, the provincial department has recently recommended routine same-day ART initiation at all its facilities.

It is unknown if same-day ART initiation among those with advanced HIV would have an adverse impact on patient outcomes at a programmatic level (as a result of unmasking IRIS). Conversely, even reflex CRAG screening may potentially delay ART initiation for those who ultimately screen CRAG negative but should be fast tracked onto ART to reduce risk of HIV progression and other OIs. We have previously described shorter median times to ART initiation amongst those CRAG-screened compared to those not screened (32).

- 4) Impact of training: We have previously implemented training workshops for health care providers (doctors, nurses, pharmacists, counsellors) with the goal of improving clinical management of cryptococcal disease. However the impact of these workshops on patient outcomes has not been measured.
- 5) Optimal treatment regimen for asymptomatic CRAG+ persons. Although CRAG+ persons receiving fluconazole generally do better than if not treated at all, 25%-30% go on to develop meningitis or die despite the WHO-recommended antifungal therapy and ART. A 2.9-fold worse survival was observed in asymptomatic CRAG+ vs. CRAG- persons with CD4 count <200 cells/µL in Tanzania and Zambia (33) (Figure 7).

The current WHO regimen for asymptomatic CRAG+ patients was based on expert opinion and extrapolated from management of symptomatic cryptococcal meningitis.

This regimen likely requires further refinement. As an example, preliminary results from the ORCAS trial in Uganda suggest that persons with CRAG titres \geq 160 and CD4 count <50 cells/µL are more likely to develop subsequent cryptococcal meningitis compared with those with a lower CRAG titre/ higher CD4 count when receiving current WHO-recommended antifungal therapy. Customized or more intensive therapy for those with high titres may be a useful strategy to reduce CRAG+ mortality (**Figure 8**).

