 - o Subset of those with cryptococcal meningitis

Primary objective (Years 2-5): To implement and test programmatic interventions to improve 6-month cryptococcal-free survival.

Starting in Year 2, we will use the data generated from the preceding years regarding the barriers in the cascade-of-care to identify areas which may require programmatic interventions to improve 6-month CRAG+ outcomes. Such interventions will be implemented at selected enhanced surveillance facilities to determine their effectiveness (pre/post intervention) as well as compared with facilities without the intervention. The exact intervention(s) to be implemented will be dependent on the challenges observed during the initial surveillance. Examples may include:

Intervention 1: Stratification by CRAG titre

For a subset of CRAG+ persons in the enhanced surveillance cohort, we will perform CRAG titres. We anticipate performing these retrospectively (batched) initially, and then for a short time prospectively to evaluate whether this is feasible in the lab. CRAG titres will not be reported to treating clinicians initially. Once data have been collected in years 1 and 2 regarding outcomes of those with high CRAG titres vs. low CRAG titres, we may then routinely report CRAG titre results with CD4 results. An information sheet may be attached to the lab results educating healthcare workers of the CRAG+ result and suggestions for management. Alternatively, this

information will be included in routine healthcare worker training materials. We may recommend that those with a CRAG titre \geq 160 have a LP performed to evaluate for meningitis, given that these persons are at high risk for meningitis and death. The outcome will be 6-month survival.

We hypothesize those with CRAG titres \geq 160 will benefit from recommended lumbar punctures to detect occult meningitis (defined as CSF CRAG+ and/or culture-positive) in comparison with those who decline LPs. Conversely, we hypothesize those with low CRAG titres <160, do not have a survival benefit when receiving LPs (i.e. due to low prevalence of asymptomatic occult meningitis).

Intervention 2: Healthcare provider training

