4.2 Subject Exclusion Criteria

• Age <18 years

Rationale for Criteria:

This project will generate an epidemiological dataset and will then explore the primary endpoint for pre-specified subgroups, along with operational challenges amongst specific subgroups.

STUDY EVALUATIONS 5

We will collect 3 types of data: patient-level, clinic-level, and laboratory-level.

Patient-level data

Chart review will occur approximately 3 times over a 6 month period, with the goal of capturing the patient-level information on CRAG+ persons. Timing of these chart reviews will be variable.

The chart abstractor will ensure that the subject has a positive CRAG result. If so, additional clinical information will be extracted from the chart (see below).

Informed consent will not be obtained for this study, as we are retrospectively collecting demographics and outcomes for CRAG+ and CRAG- patients in routine care. Please see Informed Consent section below.

Baseline demographic information will be obtained, including age, sex, date of birth, location, distance from clinic. Thereafter information about CRAG screening will be obtained. Namely, whether CRAG results were returned to the medical chart and how the healthcare provider acted on these results. If symptomatic, were they offered an LP? If asymptomatic were they prescribed fluconazole? What were the doses and dates of fluconazole therapy, and were there any side effects. Timing of initiation of ART and active treatment for TB will be obtained from the chart. Survival status, along with the date that the patient was last known to be alive will also be collected.

	ecieu
Evaluations	Monitoring Visit
CRAG+, titre	х
CD4 count	Х
Baseline demographic data	Х
If symptomatic, receipt of LP	х
If asymptomatic, receipt of fluconazole	х

Patient-level	data	to be	collected

Evaluations	Monitoring Visit
Completion of fluconazole	Х
Initiation of ART (timing)	Х
Concurrently on TB treatment	Х
Incidence of cryptococcal Meningitis	Х
6-month retention in care	х
6-month vital status	Х

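### The overall Years 2-5 comparison of event rates has no stated adjustment for patient mix, so a differential change in mix can imitate or hide an intervention effect

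*Protocol*

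**What the plan says.** The Years 2-5 primary objective is to implement and test programmatic interventions that improve 6-month cryptococcal meningitis-free survival (Protocol, Section 2.1). Section 8.1, which is headed as the statistical analysis plan, gives the analysis in two steps. First, for Years 1-2: "The rate (with 95% confidence interval) for the primary and secondary events will be estimated overall and for pre-specified subgroups". Then: "Those rates will subsequently be compared with the rates after programmatic changes have been made (during years 2-5". The only modelling it names is for a different purpose: "For the subgroups we will also use time-to-event methods to compare the primary and selected secondary endpoints".

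Section 3 gives the design of the comparison: "Such interventions will be implemented at selected enhanced surveillance facilities", and the aim is "to determine their effectiveness (pre/post intervention) as well as compared with facilities without the intervention". No random allocation of facilities is described, and the text does not say whether the two contrasts are combined into one estimate.

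On data, Section 5 (Patient-level data) states: "Baseline demographic information will be obtained, including age, sex, date of birth, location, distance from clinic". Its table adds CD4 count, titre, timing of ART and concurrent TB treatment. Section 3 (Intervention 1) limits titre testing to part of the CRAG+ cohort.

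On prognosis, Section 1.1 reports preliminary data that patients with titres of 160 or more and CD4 below 50 "are more likely to develop subsequent cryptococcal meningitis compared with those with a lower CRAG titre/ higher CD4 count". Section 3 (secondary objective on treatment failure) names high titre as a hypothesised risk factor for meningitis and death, and ART timing as another possible one.

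**The concern.** The Years 2-5 objective is judged on a non-randomised contrast. If the patients behind the two rates differ in prognosis, the difference in rates mixes that with the effect of the intervention.

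The Protocol gives reasons to think the mix could move:

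- Entry needs only a positive blood CRAG test and age 18 or over, so the cohort depends on who is tested.
- ART practice is changing (Section 1.1). This could alter how many patients are already on ART when CD4 is drawn.
- One candidate intervention, the line lists of patients with low CD4 and no CRAG result, could itself bring in patients who would otherwise have been missed, and only at intervention facilities.

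The subgroup rates help only in part. Each subgroup splits on one factor. CD4 and age are not in the list. Some listed subgroups (duration of fluconazole, secondary prophylaxis) arise after baseline and cannot correct for mix. The overall rate, on which the objective turns, stays unstandardised.

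**Working it through.** **Reproducing the Protocol's own figure.** Section 8.1 gives detectable hazard ratios for 300 high-titre against 900 low-titre patients, with 70% event-free survival in controls and two-sided alpha 0.05. Under proportional hazards, high-titre survival is 0.70^HR.

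- HR 1.37: 0.70^1.37 = 0.613. Power by the two-proportion formula is 78.7% (stated 80%).
- HR 1.44: 0.70^1.44 = 0.598. Power is 89.6% (stated 90%).

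The table is sound to within 2 points. It concerns the titre subgroup contrast. The Protocol gives no power figure for the Years 2-5 comparison. The 0.61 in the table is a detectable value and not a forecast, but it supplies the only numerical risk gap in the statistical section.

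**Bias from a mix shift with no true effect.** Bias = shift in share × risk gap.

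- From the Protocol: high-titre share 300/1200 = 25%; survival 0.61 and 0.70; gap 9 points.
- Unadjusted baseline survival = 0.25 × 0.61 + 0.75 × 0.70 = 67.75%.
- Assumed share falls to 15%: 0.15 × 0.61 + 0.85 × 0.70 = 68.65%, a change of +0.9 points.
- Assumed share rises to 35%: 66.85%, a change of −0.9 points.
- Standardised to the 25/75 baseline mix, the change is 0 in either case.

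**Effect on the error rate.** Assumed patients per period: 6000 cases a year (lower figure in Section 8.2) × 400/4500 clinics × 2 years = 1067.

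- SE of a difference = √(2 × 0.3 × 0.7 / 1067) = 1.98 points.
- Two-sided rejection probability = Φ(−1.96 + bias/SE) + Φ(−1.96 − bias/SE).

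| Assumed shift × risk gap | Bias (points) | False-positive rate |
|---|---|---|
| 10 × 9 (Protocol's titre gap) | 0.9 | about 7.4% |
| 10 × 10 | 1.0 | 8.0% |
| 15 × 15 | 2.25 | 20.5% |
| 20 × 20 | 4.0 | 52.2% |

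Only the 9-point gap comes from the Protocol. All the shifts and the other gaps are assumptions.

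**Dependence on numbers.** The next table takes a fall in high-titre share from 25% to 15%, for assumed numbers per period, using the survival in each scenario. The second row assumes HR 2.0, so high-titre survival is 0.70² = 0.49 and the bias is 10% × 21 = 2.1 points.

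| Scenario | n = 600 | 1200 | 3000 | 6000 |
|---|---|---|---|---|
| Bias 0.9 points | 6.3% | 7.6% | 11.6% | 18.5% |
| Bias 2.1 points | 12% | 19% | 40% | 68% |

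The bias is constant while the standard error falls, so the error rate rises with n. For scale, the smallest improvement on 67.75% detectable with 80% power is about 7.3, 5.2 and 3.3 points at 600, 1200 and 3000 per period. A 0.9-point bias is small beside these.

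**The case against.** The case on the other side is substantial.

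- **Silence is not a stated unadjusted analysis.** A reader might infer that the Protocol prescribes crude rates. It never says so. A separate analysis plan may name covariates, and Section 3 says the interventions themselves depend on the first years' findings. This stands as a limit on the claim. What remains is that Section 8.1 does specify the contrast for a primary objective, as a comparison of rates, and names a model only for subgroups.
- **Covariates are partly used.** The rates carried forward include those by subgroup: titre, sex, pregnancy, liver disease, urban/rural and ART timing, including pre-existing ART. This stands, but it is one factor at a time, without CD4 or age, and it does not standardise the overall rate.
- **The concurrent comparator may remove much of the bias.** Stable differences between facilities, and mix shifts common to both groups, cancel if the two contrasts are combined. This is correct. The Protocol does not say that they are combined, and a shift specific to the intervention facilities would remain.
- **No change in mix is demonstrated.** A reader might infer that the two cohorts will differ. Section 1.1 documents changing care, not a change in who tests CRAG+, and screening is confined to CD4 below 100 throughout, which limits drift in CD4. The supportable word is can, not will.
- **The leading risk factor is not available for everyone.** A reader might infer that all main prognostic factors are abstracted for every patient. Titre is run for a subset only, so adjusting for CD4 and demographics does not fully remove confounding by titre.
- **The number per period may be too high.** Interventions go to selected facilities only. A smaller n lowers the false-positive rate (6.3% at 600 with the Protocol's gap).

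**Conclusion.** The point holds in a limited form. As written, the overall Years 2-5 contrast is non-randomised and has no stated adjustment. A differential change in patient mix would pass into it, in either direction.

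On the Protocol's own titre gap and an assumed 10-point shift, the distortion is 0.9 points. At an assumed 1067 per period the false-positive rate is about 7.4% against a nominal 5%. A reader might take about 20% as the expected rate. That needs a 15-point shift and a 15-point risk gap, and the Protocol supplies neither. It shows what stronger or combined shifts could do and is not an estimate. Larger cohorts do not cure the problem, since the bias stays fixed while precision improves. The change is worth making because the baseline data are already planned and the covariates can be fixed before Years 2-5 outcomes are seen.

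**What to change.** In Section 8.1, define the main Years 2-5 estimate as a regression-standardised difference in 6-month cryptococcal meningitis-free survival that:

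- combines the before/after contrast with the concurrent-facility contrast in one model, with standard errors clustered by facility;
- adjusts for baseline CD4 count, age, sex, ART status at the CD4 draw, and TB treatment at baseline where its timing can be established;
- adds titre in a sensitivity analysis in the subset that has it;
- does not adjust for anything the intervention can change, such as fluconazole receipt or later ART timing.

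Keep the unadjusted rates, overall and by subgroup, as descriptive output beside it.

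The cost is a paragraph in Section 8.1, one model, and a rule for missing covariates. No new variables are needed. Combining the contrasts also costs precision: with four equal cells the standard error is √(4pq/n) against √(2pq/n), a factor of √2. At 1067 per cell and p = 0.7 that is 2.81 points against 1.98, before covariate adjustment or clustering. Residual confounding by titre and by unrecorded factors will remain and should be acknowledged.
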